## 2.4.4.2 Analyses of secondary efficacy endpoints

#### 2.4.4.2.1 Continuous endpoints anticipated to have a normal distribution

Continuous secondary variables defined in Section 2.1.3.2 anticipated to have a normal distribution (i.e., lipids other than TG, TGRL and Lp(a)) will be analyzed using the same MMRM model as for the primary endpoint. Specifically, the model will contain fixed categorical effects of treatment group, randomization stratum as per IVRS, planned time points to Week 24, treatment group-by-time point interaction, stratum-by-time point interaction, as well as, the continuous fixed covariates of corresponding baseline value and baseline value-by-time point interaction.

#### 2.4.4.2.2 Continuous endpoints anticipated to have a non-normal distribution

Continuous secondary efficacy endpoints defined in Section 2.1.3.2, anticipated to have a non-normal distribution (i.e., TG, TGRL, and Lp(a)); will be analyzed using a robust regression model (i.e., ROBUSTREG SAS procedure with M-estimation option) with treatment group, randomization stratum as per IVRS as main effects and corresponding baseline value(s) as covariate. Missing values will be addressed using a multiple imputation model. The imputation model will include:

- The variables included in the robust regression model, i.e. the treatment group, the randomization stratum, and the baseline value.
- The baseline characteristics such as: age, BMI, and gender. Age and BMI will be included as continuous variables.
- The values at Week 8, Week 12, Week 20 and Week 24 time points.

Non continuous variables included in the imputer's model (i.e., treatment group, randomization stratum, and gender) are not expected to be missing.

In the robust regression model, the analyzed endpoint at time point of interest will be derived from observed and imputed lipid values at this time point. The treatment group combined means will be provided with respective SE estimates. The combined mean difference between the treatment groups will be provided with the SE, 97.5% CI and p-value through the SAS MIANALYZE procedure.

## 2.4.4.2.3 Binary endpoints

Binary secondary efficacy endpoints defined in Section 2.1.3.2 (e.g., proportion of patients below a threshold) will be analyzed using logistic regression with treatment group and randomization stratum as per IVRS as main effects and corresponding baseline value(s) as covariate. Missing values will be addressed using a multiple imputation approach (see Section 2.4.4.2.2). The variables in the multiple imputation model will at least include the same variables as used in the logistic regression model. In the logistic regression model, the analyzed endpoint at time point of interest will be derived from observed and imputed lipid values at this time point. Treatment effects will be compared and the combined odds ratio estimate between the treatment groups, with their corresponding 97.5% CI and p-value will be provided via the SAS MIANALYZE procedure.

In the data dependent case that the logistic regression method is not applicable (e.g., the response rate is zero in one treatment arm and thus the maximum likelihood estimate may not exist), the last observation carried forward (LOCF) approach would be used for handling of missing values and an exact conditional logistic regression would be performed to compare treatment effects. The LOCF imputation method will consist of using the last value obtained up to the Week 24 analysis window (or Week 12 as applicable) to impute the missing Week 24 value (or Week 12 respectively).

In case of computing issues with exact logistic regression, the baseline level(s) will be entered in the model as a categorical variable(s) using quartiles. Exact odds ratio versus usual care, 97.5% CI, and p-value will be provided.

#### 2.4.4.2.4 Summary of results per time point

Central laboratory values (in conventional and international units), percent change from baseline and/or when appropriate, absolute change from baseline (in conventional and international units) of all lipid efficacy endpoints (as listed in Section 2.1.3) will be provided at each time point and for each treatment group in the ITT population using:

- For lipids other than TG, TGRL, and Lp(a): LS mean and SE for each treatment group, obtained from the same MMRM models as used for endpoints above and including all planned time points and with raw values, changes from baseline, or percent change from baseline as response variable in the model as appropriate.
- For TG, TGRL and Lp(a): combined mean and SE for each treatment group obtained from multiple imputation approach followed by the robust regression models as used for endpoints above and including all planned time points and with raw values or percent changes from baseline as response variable in the model as appropriate.

All measurements, scheduled or unscheduled will be assigned to analysis windows (see Section 2.5.3 on which value to select) in order to provide an assessment for these time points. Laboratory assessments other than the ones provided by the central laboratory will be excluded.

Summary tables and graphs over time for each parameter will be plotted by treatment group (LS mean + SEs by time point).

Property of the Sanofi Group - strictly confidential

26-Apr-2017

In addition, quantitative descriptive summaries by time point for each treatment group (value at visit and % change from baseline, and/or when appropriate absolute change from baseline) will be presented for all lipids using observed (i.e., non-missing) data and binary variables will be also provided in summary tables.

Non-HDL-C will be summarized and plotted according to up-titration status. i.e., according to whether the patients remained on the 75 mg dose or whether they were up-titrated to 150 mg.

#### 2.4.4.3 Sensitivity analysis for the computation of TGRL values

Two sensitivity analyses will be performed to assess the impact of the computation of TGRL values on the effect of treatment:

- 1. In the first sensitivity computation, TGRL will be computed from measured LDL-C only, not replaced by calculated LDL-C in case of missing value for measured LDL-C.
- 3. In the second sensitivity computation, TGRL will be computed from fasting samples only, i.e. non-fasting samples will be excluded from analysis.

For both sensitivity computations, the percent change from baseline to Weeks 12 and 24 will be assessed in the same way than for the main computation of TGRL, using the model described in section 2.4.4.2.2.

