## 9.2.5.2.3 Bioanalytical method

#### 9.2.6 Other efficacy endpoints (ITT estimand)

- Percent change in calculated LDL-C from baseline to Weeks 12 and 24.
- Percent change in Apo B, Total-C, Lp(a), TGs, HDL-C from baseline to Week 12.
- Proportion of patients reaching measured LDL-C <50 mg/dL (1.30 mmol/L), <70 mg/dL (1.81 mmol/L) and < 100 mg/dL (2.59 mmol/L) at Weeks 12 and 24.
- Percent change in measured LDL-C according to baseline TGs of <median TG or ≥median TG at Weeks 12 and 24.
- Proportion of patients reaching non-HDL-C <130 mg/dL (3.37 mmol/L), <100 mg/dL (2.59 mmol/L) and <80 mg/dL (2.07 mmol/L) at Weeks 12 and 24.

- Percent change in TGs from baseline to Weeks 12 and 24 according to baseline TGs of <median TG or ≥median TG.
- Percent change in LDL particle number from baseline to Week 12.
- Percent change in LDL particle size from baseline to Weeks 12 and 24.
- Percent change in VLDL, HDL and IDL particle number from baseline to Weeks 12 and 24.
- Percent change in Apo A-1 and Apo-C-III from baseline to Weeks 12 and 24.
- Absolute change in TGRLs (ie, non-HDL-C minus LDL-C) from baseline to Weeks 12 and 24.
- Proportion of patients with 50% or greater reduction from baseline in measured LDL-C at Weeks 12 and 24.
- The proportion of patients reaching Apo B < 80 mg/dL at Weeks 12 and 24.
- Absolute change in ratio Apo B/Apo A-1, Total-C/HDL-C and LDL-C/HDL-C from baseline to Weeks 12 and 24.

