### 2.1.3.2.3 Other efficacy endpoints (ITT estimand)

- Percent change in calculated LDL-C from baseline to Weeks 12 and 24
- Percent change in Apo B, Total-C, Lp(a), TGs, HDL-C from baseline to Week 12
- Proportion of patients reaching measured LDL-C <50 mg/dL (1.30 mmol/L), <70 mg/dL (1.81 mmol/L) and <100 mg/dL (2.59 mmol/L) at Weeks 12 and 24
- Percent change in measured LDL-C according to baseline TGs of <median TG or ≥median TG at Weeks 12 and 24
- Proportion of patients reaching non-HDL-C <130 mg/dL (3.37 mmol/L), <100 mg/dL (2.59 mmol/L) and <80 mg/dL (2.07 mmol/L) at Weeks 12 and 24
- Percent change in TGs from baseline to Weeks 12 and 24 according to baseline TGs of <median TG or >median TG
- Percent change in LDL particle number from baseline to Week 12
- Percent change in LDL particle size from baseline to Weeks 12 and 24
- Percent change in VLDL, HDL and IDL particle number from baseline to Weeks 12 and 24
- Percent change in Apo A-1 and Apo C-III from baseline to Weeks 12 and 24

- 26-Apr-2017 Version number: Final
- Absolute change in TGRLs (non-HDL-C minus measured LDL-C if measured LDL-C not missing; non-HDL-C minus calculated LDL-C if measured LDL-C missing and calculated LDL-C not missing, using fasting samples first, or if fasting sample missing using nonfasting measurements) from baseline to Weeks 12 and 24
- Proportion of patients with 50% or greater reduction from baseline in measured LDL-C at Weeks 12 and 24.
- Proportion of patients reaching Apo B <80 mg/dL at Weeks 12 and 24.
- Absolute change in ratio Apo B/Apo A-1, Total-C/HDL-C and LDL-C/HDL-C from baseline to Weeks 12 and 24.

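### Both TGRL sensitivity computations are planned on percent change, so the declared absolute-change endpoint has no sensitivity analysis on its own scale

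*SAP*

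**What the plan says.** Protocol 9.2.6 lists among the other efficacy endpoints "Absolute change in TGRLs (ie, non-HDL-C minus LDL-C) from baseline to Weeks 12 and 24", and the protocol synopsis has the same definition. SAP 2.1.3.2.3 keeps the scale and adds the data rule: "Absolute change in TGRLs (non-HDL-C minus measured LDL-C if measured LDL-C not missing", otherwise calculated LDL-C, with fasting samples taken first and non-fasting samples used only if no fasting sample exists.

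SAP 2.4.4.2.2 covers the secondary endpoints of SAP 2.1.3.2 that are expected to have a "non-normal distribution (i.e., TG, TGRL, and Lp(a)); will be analyzed using a robust regression model" after multiple imputation. It names no response scale of its own.

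SAP 2.4.4.3 gives the purpose of the extra work: "Two sensitivity analyses will be performed to assess the impact of the computation of TGRL values on the effect of treatment". The first computation uses measured LDL-C only. The second uses fasting samples only. The response is then stated: "the percent change from baseline to Weeks 12 and 24 will be assessed in the same way" as the main computation, with the model of 2.4.4.2.2.

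SAP 1.5 and 1.6, which would record statistical modifications, both read not applicable.

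**The concern.** A sensitivity analysis of a computation rule should change that rule and hold everything else fixed. Here two things change relative to the declared endpoint: the rule for deriving TGRL, and the response scale. If the declared result and a sensitivity result differ, the reader cannot tell from those two numbers which change caused it. If they look alike, the agreement is between an effect in mg/dL and an effect in percentage points. What is at stake is whether the declared TGRL result can be called robust to the use of calculated LDL-C and non-fasting samples, which is the question that 2.4.4.3 sets itself.

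**Working it through.** The documents state no figure on this point, so there is none to reproduce. The check is mainly a comparison of sections.

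**Scale by section**

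| Place | Scale for TGRL |
|---|---|
| Protocol synopsis; protocol 9.2.6 | absolute change |
| SAP 2.1.3.2.3 | absolute change |
| SAP 2.4.4.2.2 (model) | none named; points to the endpoints of 2.1.3.2, hence absolute change |
| SAP 2.4.4.3 (both sensitivity computations) | percent change |
| SAP 2.4.4.2.4 (model-based summaries by time point) | "with raw values or percent changes from baseline as response variable in the model as appropriate" |
| Protocol 11.4.2.2 (descriptive tables) | TGRL is listed; absolute change appears to be meant for the ratio and percent change for the rest |

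The main analysis is therefore on absolute change by cross-reference, and both sensitivity computations are on percent change by explicit statement. No section reconciles the two.

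**Can one scale be converted to the other?** Let B be baseline, W the on-study value, T treatment.

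- Absolute change: W − B = a + τT + bB + e. Adding B to both sides gives W = a + τT + (b + 1)B + e, with the same residuals. With baseline as a covariate, raw values and absolute change therefore give the same treatment difference τ. Adding stratum terms does not alter this.
- Percent change: 100(W − B)/B divides each patient's change by that patient's own baseline. No single factor converts its treatment effect to τ.

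A constructed two-patient example shows that the summaries can part company. TGRL goes from 20 to 30 and from 60 to 45 mg/dL.

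- Mean absolute change: (10 − 15)/2 = −2.5 mg/dL.
- Mean percent change: (50 − 25)/2 = +12.5%.

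**Illustration at trial size.** The documents give 280 versus 140 patients and 97.5% confidence intervals (two-sided 0.025). They give no TGRL distribution or effect, so the following are assumptions: log-normal baseline with median 30, 40 or 50 mg/dL and log-SD 0.3 or 0.5; W = B × exp(−0.05 − 0.10T + 0.35Z), with Z standard normal. A Huber M-regression on treatment and baseline was fitted on both scales to the same complete data, with no stratum term and no imputation, in 400 replicates per row.

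| Median, log-SD | Absolute effect (mg/dL) | Percent effect (points) | Verdicts at 0.025 differ |
|---|---|---|---|
| 30, 0.3 | −2.67 | −8.87 | 6.0% |
| 30, 0.5 | −2.60 | −8.74 | 11.3% |
| 40, 0.3 | −3.63 | −9.02 | 6.0% |
| 40, 0.5 | −3.58 | −8.98 | 10.7% |
| 50, 0.3 | −4.63 | −9.17 | 4.5% |
| 50, 0.5 | −4.48 | −8.87 | 8.0% |

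The simulation error of the last column is about 1.0 to 1.6 points: √(0.045 × 0.955/400) = 0.010 and √(0.113 × 0.887/400) = 0.016. With no change at all in how TGRL is computed, the change of scale alone moved the significance verdict in 4.5% to 11.3% of simulated trials. It left the verdict unchanged in 88.7% to 95.5%.

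**The case against.** The strongest reply is that a reader might infer from the mismatch that the planned analyses can say nothing about robustness, and the documents do not support that. SAP 2.4.4.3 ties the sensitivity computations to the method of the main computation, and 2.4.4.2.4 permits percent change for TGRL from the same kind of model. Protocol 11.4.2.2 also appears to place TGRL among the percent-change tables. If a percent-change result for the main computation is produced, comparing percent with percent isolates the data rule. That stands. The evidence is nonetheless indirect, because it concerns an undeclared scale and the declared estimate still has no counterpart.

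Two further inferences should be resisted. One is that percent change in TGRL is too unstable to use. The documents give no TGRL distribution, the 30 mg/dL cut in the SAP is a category boundary and not an expected baseline, entry requires screening triglycerides of at least 150 mg/dL, and M-estimation downweights outlying responses. The other is that 2.4.4.2.4 must also be rewritten. Its TGRL bullet does omit the change-from-baseline option that the bullet for the other lipids has ("with raw values, changes from baseline, or percent change from baseline as response variable in the model as appropriate"). But its opening paragraph already allows absolute change where appropriate, and raw values with baseline as covariate give the same treatment difference, as shown above.

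The practical stakes are also small. Measured LDL-C is scheduled at every lipid visit, and protocol section 10 says blood is not to be drawn from patients who are not fasting. Both sensitivity datasets should therefore differ from the main one in few samples.

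**Conclusion.** The mismatch is real and follows from the text alone. The declared TGRL endpoint is absolute change, both sensitivity computations are specified on percent change, and no modification is recorded. The declared result therefore has no sensitivity analysis on its own scale and cannot be compared directly with the two planned estimates.

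The impact is minor. TGRL is outside the primary endpoint and the key secondary hierarchy, and under SAP 2.4.4.4 its p-values are descriptive. The simulated discordance shows only that the scales are not interchangeable; it rests on assumed distributions and does not estimate the effect on this trial. The documents do not say whether the percent wording was intended. It may have been carried over from the triglyceride and Lp(a) endpoints, which are declared as percent change.

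**What to change.** In the closing sentence of SAP 2.4.4.3, make the response the absolute change from baseline to Weeks 12 and 24 for both computations, with the multiple imputation and robust regression of 2.4.4.2.2 unchanged. If percent change is still wanted, label it supplementary and present it beside the percent-change result of the main computation, so that each comparison is made within one scale. If the sponsor in fact intended percent change as the endpoint, the endpoint definition is what has to be amended, and the change recorded in SAP 1.6.

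The cost is one wording change and a rerun of an already specified model for two computations at two time points, with no new data. It is best made before database lock, so that the scale is not chosen after the results are seen. SAP 2.4.4.2.4 needs no change for this purpose.

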## 2.4.4.4 Multiplicity issues

In order to handle multiple key secondary efficacy endpoints (for both analyses, i.e. alirocumab versus usual care and alirocumab versus fenofibrate), the overall type-I error (0.025 for each analysis) will be controlled by the use of a sequential inferential approach. Statistical significance of the primary parameter at the 0.025 alpha level is required before drawing inferential conclusions about first key secondary parameter (refer to order in Section 2.1.3.2.1).

Inferential conclusions about successive key secondary efficacy parameters require statistical significance of the prior one. This fixed hierarchical approach will ensure a strong control of the overall type-I error rate at the 0.025 level for each analysis (alirocumab versus usual care and alirocumab versus fenofibrate).

No further adjustments will be made for other efficacy endpoints for which p-values will be provided for descriptive purpose only.

#### 2.4.4.5 Additional efficacy analyses

All analyses of the efficacy endpoints (primary, key secondary and other efficacy endpoints) will also be performed within each other randomization stratum as per IVRS (no additional LMT, or intent to prescribe ezetimibe, omega-3 fatty acids, or nicotinic acid) in order to compare the efficacy of alirocumab versus the other options of usual care. The analyses will be similar to the ones performed for the fenofibrate stratum (see Section 2.4.4.1.1) provided that there are at least 10 patients in each treatment arm in the stratum of interest.

Additional efficacy analyses on selected endpoints will also be replicated in the subgroup of patients of the region North America.

#### 2.4.5 Analyses of safety data

The summary of safety results will be presented by actual treatment group. Summaries will be descriptive in nature. Safety analyses will be performed overall and by actual stratum defined by the actually received treatment (only for strata with at least 10% of patients).

#### General common rules

All safety analyses will be performed on the safety population as defined in Section 2.3.2, unless otherwise specified, using the following common rules:

- Safety data in patients who do not belong to the safety population (e.g., exposed but not randomized or re-randomized patients) will be listed separately.
- The baseline value is defined generally as the last available value before the first injection of open-label alirocumab/first dose of usual care treatment for patients prescribed another LMT if allocated to the usual care arm/ randomization for patients randomized to usual care and not receiving additional LMT.
- The PCSA values are defined as abnormal values considered medically important by the Sponsor according to predefined criteria/thresholds based on literature review and defined by the Sponsor for clinical laboratory tests and vital signs (PCSA version dated January 2009 [Appendix A]).
- PCSA criteria will determine which patients had at least one PCSA during the TEAE period, taking into account all evaluations performed during the TEAE period, including nonscheduled or repeated evaluations. The number of all such patients will be the numerator for the on-treatment PCSA percentage.
- The treatment-emergent PCSA denominator by group for a given parameter will be based on the number of patients assessed for that given parameter in the TEAE period by treatment group on the safety population.
- All measurements, scheduled or unscheduled, fasting or not fasting, will be assigned to analysis windows defined in Section 2.5.3 in order to provide an assessment for Week 0 to Week 24 time points.
- For quantitative safety parameters based on central laboratory measurements, descriptive statistics will be used to summarize results and change from baseline values by visit and treatment group using analysis windows. Summaries will also include the last on-treatment value and the worst on-treatment value. The last on-treatment value is defined as the last value collected during the treatment period (see Section 2.1.4). The worst on-treatment value is defined as the nadir and/or the peak value during the treatment period according to the direction (minimum or maximum) of the abnormality as defined in the PCSA list.
- For exploratory purpose, all TEAE analyses will be provided according to up-titration status, i.e., according to whether the patients remained on the 75 mg dose or whether they

were up-titrated to 150 mg. These analyses will be exploratory and descriptive (no formal comparison per dose) as it is expected that there could be inherent differences in the baseline characteristics between those patients titrating to 150 mg and those remaining on 75 mg. In order to reduce the bias of this analysis, the period before the up-titration time point (planned at Week 12) will be analyzed separately since only the dose 75 mg is proposed for this time period and consequently the early events occurring before Week 12 can only be attributed to this dose. Therefore the descriptive analysis per dose will include any safety events occurring from the first injection post Week 12 IVRS/IWRS transaction to the end of the TEAE period. Baseline characteristics of patients receiving each dose will be summarized.

#### 2.4.5.1 Analyses of adverse events

#### **Generalities**

The primary focus of AEs reporting will be on TEAEs. Pre-treatment and post-treatment AEs will be described separately.

If an AE date/time of onset (occurrence, worsening, or becoming serious) is incomplete, an imputation algorithm will be used to classify the AE as pre-treatment, treatment-emergent, or post-treatment. The algorithm for imputing date/time of onset will be conservative and will classify an AE as treatment emergent unless there is definitive information to determine it is pre-treatment or post-treatment. Details on classification of AEs with missing or partial onset dates are provided in Section 2.5.2.

Adverse event incidence tables will present, the number (n) and percentage (%) of patients experiencing an AE by SOC, HLGT (when applicable), HLT (when applicable), and PT. Multiple occurrences of the same event in the same patient will be counted only once in the tables within a treatment phase. The denominator for computation of percentages is the safety population within each treatment group.

Sorting within tables ensures the same presentation for the set of all AEs within the observation period (pre-treatment, treatment-emergent, and post-treatment). For that purpose, the table of all TEAEs presented by SOC and PT sorted by the internationally agreed SOC order and decreasing frequency of PTs within SOCs (in the alirocumab group) will define the presentation order for all other tables unless otherwise specified. The tables of AEs by SOC, HLGT, HLT, and PT will be sorted by the internationally agreed SOC order and the other levels (HLGT, HLT, PT) will be presented in alphabetical order, unless otherwise specified.

